1 REVISIONS

Version	Date	Summary of changes
0.5	30 Nov. 23	Initial draft
1.0	30 Oct. 24	Finalised version

2 GENERAL

2.1 Document scope

The current document describes the planned analyses of economic evaluation alongside the ComBAT randomised controlled trial (RCT).

This analysis plan has been checked for consistency with the ComBAT RCT trial protocol v4 (25 Sept 2023).

2.2 Glossary

AIC	Akaike Information Criterion
BA	Behavioural activation
BIC	Bayesian Information Criterion
CAMHS	Child and adolescent mental health services
CBT	Cognitive behavioural therapy
CCA	Cost consequence analysis
CDRS-R	Children's depression rating scale - revised
CEA	Cost-effectiveness analysis
CEAC	Cost-effectiveness acceptability curves
CHU-9D	Child health utility – 9 dimensions
ComBAT	Community-based behavioural activation training

CWP	Children's wellbeing practitioner
CYP IAPT	Children and young people's improving access to psychological therapies
IAPT	Improving access to psychological therapies
ICER	Incremental cost-effectiveness ratio
IPT	Interpersonal therapy
LA	Local authority
MAR	Missing At Random
MI	Multiple imputation
MNAR	Missing Not At Random
MOOC	Massive open online courses
NHS	National Health Service
NICE	National Institute for Health and Care Excellence
PHQ-9A	Patient Health Questionnaire – Modified for Adolescents
PSS	Personal Social Service
QALY	Quality-adjusted Life Year
RCT	Randomised controlled trial
RCADS	Revised Childrens' Anxiety and Depression Scale
RUQ-A	Resource utilisation questionnaire for adolescents
SAP	Statistical analysis plan
YTU	York Trials Unit

3 TRIAL SUMMARY

The following sections briefly describe the ComBAT RCT. For full details please see the protocol (v4, 25/09/2023).

3.1 Aim and objectives

The aim of the economic evaluation is to establish the cost-consequences of a community-based behavioural activation training (ComBAT) for depression in adolescents compared with usual care.

Specific objectives are:

- To describe the components and estimate the costs of ComBAT;
- To assess the impact of ComBAT on entry to Child and Adolescent Mental Health Services (CAMHS) compared to usual care at 6 and 12 months post-randomisation;
- To conduct a cost-consequence analysis of ComBAT compared with usual care for the National Health Service (NHS) and Personal and Social Service (PSS) and for the education sector;
- To conduct an incremental cost-effectiveness analysis of ComBAT compared with usual care from the mental health service perspective at 6 months post-randomisation (primary outcome timepoint).

3.2 Design

The ComBAT RCT is a parallel two-group randomised controlled trial with allocation at the level of individual. The trial is being delivered in a variety of services responsible for providing support to young people with mild to moderate depression. These include NHS services such as CAMHS, school-based or other community-based services. These sites are involved in the identification of study participants and are the locations for intervention delivery.

The inclusion criteria of participants are: 1) aged 12-18 years at the date of consent; 2) score ≥ 65 on the depression subscale (10-items) of the Brief version of the Revised Children's Anxiety and Depression Scale (RCADS); 3) scores < 15 on the Patient Health Questionnaire – Modified for Adolescents (PHQ-9A); 4) provide consent, or assent along with their parent's consent (if applicable), to participate in the study.

The PHQ-9A is being used to screen for depression severity and suicide risk. If a young person scores ≥ 15 in the sum of the 9 items (indicating severe depression), or responds “more than half-days” or “nearly every day” on question 9 and/or yes to SQ3 and SQ4, they will be invited to speak with a clinical member of the ComBAT team to confirm their eligibility for entry to the study, or be signposted to other services as necessary.

Participants are excluded if they have severe depression or an increased risk of suicide; meet criteria for secondary care (tier 3/high intensity therapy) for reasons other than risk of suicide or severity of the depressive symptoms, such as a learning disability or complex comorbid conditions; cannot speak English and do not have a carer or other designated adult to translate the intervention and research materials, and to translate conversations during sessions with a professional.

The sample size is set at 236. Participants are randomised to either group at 1:1 ratio, using simple randomisation. Randomisation is implemented using a web-based system designed and developed by the data management team at York Trials Unit (YTU).

After baseline, follow-ups are conducted at 6- and 12-months post-randomisation. The measures related to the economic evaluation are presented in the following section. For a detailed schedule of all measures please see protocol (V4; 25/09/2023).

4 OUTCOMES AND DATA COLLECTION

4.1 Costs

As ComBAT may impact multiple stakeholders beyond the health care system, the costs include those incurred by the NHS/PSS and by non-NHS/PSS organisations and society in general.

4.1.1 Intervention and comparator costs

4.1.1.1 Intervention costs

Intervention costs include costs of training and costs of delivery. The relevant cost components and service use will be recorded by the research team alongside the progress of the trial to support a bottom-up approach.

The training of ComBAT support workers is arranged with sites at an appropriate time and location. It is planned to take 6 hours and delivered in one day by members of the study team. The number of trainers is selected relative to the number of attendees. As the sites are recruited and open at different times, the training has to be delivered separately on several occasions in person or online. The training manual and role play explanations are given to attendees in hard copy or via email. The fees of training venue, refreshments, printing and transportation are recorded as they occur.

The attendees are encouraged to complete, before or after the training, the online MOOC course: The Introduction to Behavioural Activation for Depression (<https://www.futurelearn.com/courses/introduction-to-behavioural-activation-for-depression>), which was developed by the study team and is free of charge. The MOOC course is designed to be completed over 3 weeks, with study time of 4 hours per week. The MOOC is hosted on the FutureLearn platform, the subscription of which is covered by University of York as an organisation. It is therefore free of charge for individual course developers within the University. There is no licence fee required for any part of the content. The course was produced previously during the feasibility study stage, no further costs were incurred thereafter.

After the initial training, attendees will be encouraged to take up supervision as much as they would like to. The supervision will be held in both group and individual formats, according to attendees' preferences. Two clinical members of the study team will act as supervisors. Supervision sessions are expected to take approximately one hour per session, regardless of whether they are delivered to an individual or group. Refresher training will be provided if necessary. These sessions will be recorded as they occur.

The intervention delivery is organised in 5 modules which can be completed in up to 8 weekly sessions of 30-40 minutes each in a blended model of professional-guided sessions and self-directed activities. The participants are encouraged to keep a log of each activity that they complete.

All other costs will be estimated based on the study team records. The opportunity costs of time for both trainers and the ComBAT support workers will be estimated by multiplying their respective hourly costs by the time they spent on the training. The hourly costs of trainers and ComBAT support workers will be identified by recording their wage bands or professional roles, plus associated salary oncosts, and overheads. As our rationale behind the study is that BA could be delivered by professionals who are less expensive to employ, the expected pay level of ComBAT support workers is below NHS pay grade 7 or non-NHS equivalent. Depending on the organisation and its locality, the ComBAT support workers may be a mixture of NHS and non-NHS employees.

4.1.1.2 Comparator costs

The comparison group in the ComBAT RCT is usual care. Usual practice for child and adolescent mental health can be widely varied and inconsistent. It may be no intervention,

signposting to alternative sources of support, general discussion, supportive counselling, relaxation, recreation groups, guided self-help or psychological therapies including CBT and IPT. Professionals involved in usual care, in turn, vary greatly by support/treatment as well as from one service to another.

We therefore do not pre-specify a standard usual care. Instead, participating professionals in the usual care arm are asked to complete a session record at each session to outline what approaches they have taken. Where usual care involves signposting young people to external support, professionals are asked to provide information about this (i.e. where the young person was signposted to).

A set of national average unit costs of the support/treatment options will be compiled from published secondary sources of the appropriate year (1-3) and applied to the quantities collected to estimate the costs of usual care.

4.1.2 Healthcare, community, social and school services costs

Healthcare services use is collected using a bespoke self-reported resource use questionnaire for adolescents (RUQ-A). The RUQ-A is administered as part of the case report form (CRF) to the participants at baseline, 6- and 12-months post randomisation.

The services in public sectors included are: general health and community services (GP, practice nurse, community paediatrician, NHS 111 call, NHS Walk-in centre, health visitor, children's centre, social worker/family support worker, online or telephone counselling), school services (teacher, school nurse, school counsellor), CAMHS (psychiatrist, psychological therapist, psychologist, mental health nurse, family therapist), and NHS hospital services (Accident & Emergency/Urgent care, inpatient ward, outpatient clinic). For all the service categories we allow an open question for participants to provide additional services within the category they use. We also collected name, dose, and start/end date of any medications taken for mental health.

A set of national average unit costs of the listed services will be extracted from published secondary sources of the appropriate year (1-3) and applied to the quantities collected to estimate the costs of healthcare and community services for mental health.

The services in the private sector are not pre-specified. Participants are asked about the name, number of uses and the amount paid for the services they have used.

4.2 Effectiveness measures

Multiple effectiveness measures are collected to provide meaningful results for different stakeholders. All measures are administered as part of the CRF at baseline, 6- and 12-months post-randomisation.

4.2.1 Revised Children's Anxiety and Depression Scale (RCADS) – Brief Version – 25 items

The primary outcome of the ComBAT RCT is depressive symptoms measured by RCADS at 6 months post-randomisation. The RCADS brief version is a 25-item questionnaire that assesses children's depression and anxiety, which is a condensed version of the original 47-item (4) and has been validated as a self-completed outcome measure for 8-to-18-year-olds. Both versions of the RCADS have sub-scales that capture symptoms in 6 domains: depression, generalised anxiety disorder, panic disorder, obsessive compulsive disorder, separation anxiety disorder and social anxiety. All items are rated on a 4-point Likert-scale from 0 to 3 (0 = Never, 1 = Sometimes, 2 = Often, and 3 = Always). Raw scores are transformed into t-scores by matching the raw score to its corresponding age and gender normed t-scores (available on the measure's website

<https://www.childfirst.ucla.edu/resources/>). Higher t-scores denote greater clinical need.

Clinical cut-offs for the t-scores are: 0-64 non-clinical range, 65-69 borderline clinical range, and ≥ 70 clinical range.

4.2.2 Quality-Adjusted Life Years

The Child Health Utility – 9 Dimensions (CHU-9D) (5) is used to derive health gain in quality-adjusted life years (QALYs). The questionnaire consists of 9 domains, each with 5 statements (scored 1–5) that assess the young person's functioning “today” across domains of worry, sadness, pain, tiredness, annoyance, school, sleep, daily routine and activities. For example: 1= I don't feel sad today, 2=I feel a little bit sad today, 3=I feel a bit sad today, 4=I feel quite sad today, 5=I feel very sad today. The responses under the 9 domains can be taken together as a description of the young person's “health state” that combines all responses across all items (e.g. 11232152). Different utility weights are assigned to each level of each domain. Different combinations of responses across the 9 dimensions therefore result in different health states that have a utility value on a 0–1 scale, where 1 is perfect health and 0 is equivalent to being dead. The UK young people valuation set will be used to derive the utility values (6).

4.2.3 Days absent from school, training or work

The RUQ-A also includes questions about participants' days absent from school, training or work due to health worries, and days of work that their family members have taken to look after them. These would not be quantified in monetary terms.

5 ANALYSIS

5.1 Methods overview

All analyses will be carried out following an intention-to treat principle. We will attempt to present all monetary outcomes in pound sterling 2024, provided all public sources of service use are available at the time of analysis. If by the time of analysis, data of year 2024 remain unavailable, all monetary outcomes will be presented in pound sterling 2023. Discounting is not undertaken as the costs and outcomes cover a period of one year only.

We will use Excel for data compilation of intervention and usual care costs. The resulting dataset will be merged with data from the CRFs and cleaned using the latest available version of Stata. The descriptive statistics will be generated in Stata. The multi-level regression analysis will be conducted using MLwiN 3.14 (7).

The descriptive statistics of the data will be presented by time point and group. The missing data pattern will be examined at this stage. Missing data will be handled primarily using multiple imputation on the assumption of missing at random (see 5.2 below). We will carry out a cost-consequence analysis (CCA) of the ComBAT intervention compared to usual care due to the multiplicity of stakeholders and the need to present a comprehensive picture of costs and consequences from different perspectives. We will also conduct a within-trial incremental cost-utility analysis from the NHS and PSS perspective (8).

5.2 Missing data

Missing data level will be described for all measures at all time points by groups and in total. Missing data patterns will be described accordingly.

Missing data will be handled based on the framework proposed by Faria et al (9). Missing values of baseline data are expected to be rare and unrelated to the group allocation. These missing values will be imputed by the mean of the measure of the pooled sample of both groups (10).

Missing values of data at follow-ups will be handled using multiple imputation with chained equation method, following Rubin's rule and assuming missing at random (MAR) (11). The association of missingness of each measure with group allocation and baseline covariates, and with observed values of the same measure at other follow-up points will be examined using statistical tests (univariate logistic regression for continuous and binary variables, χ^2 tests for discrete variables) with 0.05 as significant level. An imputation model will be developed, including all the measures necessary for the analysis or associated with missingness identified by the statistical tests. The number of imputation will be set as approximately the highest percentage figure of the missing data (10). The imputation will be performed by allocation groups.

All analyses will be conducted on the imputed dataset, unless otherwise specified.

5.3 Primary analysis

The primary analysis will be a cost-consequence analysis (CCA) of ComBAT compared to usual care over 12 months from NHS/PSS perspective and the education perspective.

Total costs include costs of intervention and usual care, and costs of healthcare, school-based care, community care and social services for mental health over 12 months. The costs from NHS/PSS perspective and from the education perspective will be presented both separately and in total. The effectiveness measures are QALYs and number of days absent from school/work/training over 12 months. Both incremental costs and incremental QALYs will be estimated using linear regression, adjusting for costs and utility values at baseline respectively and other baseline covariates that show a significant association ($p<0.05$) with dependent variables. The difference in number of absent days will be estimated similarly, using linear regression. The appropriate models will be selected based on AIC and BIC information criteria. A Likelihood Ratio test will be used to indicate if random effects should be considered. The incremental cost-effectiveness ratios (ICERs) will be calculated by dividing the incremental costs by incremental outcomes, when both are positive.

Uncertainty around the point estimate will be assessed using the non-parametric bootstrap resampling technique (12). Bootstrapping is an efficient method for calculating the confidence limits for variables possibly deviating from normality, as its validity does not depend upon any specific form of underlying distribution. We will use bootstrapping to generate 5,000 replicates of the sample with replacement to create a distribution for incremental costs and outcomes. The 95% CIs for incremental costs and outcomes based on the bootstrapping

results will be derived using the 2.5th and 97.5th percentiles of their respective distribution. Multiple cost-effectiveness planes will be plotted using 5,000 pairs of incremental costs and corresponding incremental outcomes with four quadrants indicating four scenarios of cost-effectiveness (more costly more effective, more costly less effective, less costly more effective, less costly less effective). Cost-effectiveness acceptability curves (CEACs) (13) will be constructed based on the bootstrap iterations to estimate the probability that ComBAT is cost-effective at different threshold values, compared to usual care. Incremental costs per QALY gained from NHS/PSS perspective will be compared with the maximum acceptable threshold of ICER recommended by NICE (8). No official thresholds are available from education perspective so no conclusion will be drawn.

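### The primary cost total can count trial-treatment contacts twice, in an unknown direction, and on the natural reading omits support workers' MOOC time, which understates ComBAT cost

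*SAP*

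**What the plan says.** **Cost total.** Section 5.3 adds treatment costs and service costs: "Total costs include costs of intervention and usual care, and costs of healthcare, school-based care, community care and social services for mental health".

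**Sources of the two parts.**
- ComBAT (section 4.1.1.1): "The relevant cost components and service use will be recorded by the research team alongside the progress of the trial".
- Usual care (section 4.1.1.2): "participating professionals in the usual care arm are asked to complete a session record at each session". The section's list of possible usual care runs from nothing at all to counselling, CBT and IPT.
- Everything else (section 4.1.2): "Healthcare services use is collected using a bespoke self-reported resource use questionnaire for adolescents (RUQ-A"). Its items include "CAMHS (psychiatrist, psychological therapist, psychologist, mental health nurse, family therapist") and "school services (teacher, school nurse, school counsellor"), together with online or telephone counselling and an open item in each category.

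Section 3.2 places the trial in CAMHS, school and community services. Section 5.1 merges the treatment-cost file with the case report form data and mentions no reconciliation of the two.

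**MOOC.** Section 4.1.1.1 encourages support workers to take an online course on either side of the training day. The course is "designed to be completed over 3 weeks, with study time of 4 hours per week". The section then covers platform, licence and production costs and finds none to charge. Trainers' and workers' time is valued by "multiplying their respective hourly costs by the time they spent on the training". The training is planned as one 6-hour day.

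**The concern.** Staff of the kinds named in the RUQ-A may themselves deliver trial treatment. A course of CBT from a CAMHS therapist, or supportive counselling from a school counsellor, can be recorded by the professional at each session and reported again by the young person at 6 months. ComBAT sessions can be reported again too, under a listed item or an open one. Section 5.3 adds the two streams and gives no rule for removing the overlap.

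The MOOC raises a different question. The plan's own principle is opportunity cost, and a course with no fee still uses paid staff time.

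Both points enter incremental cost directly. That figure is reported in the cost-consequence analysis whether or not an ICER is formed, and it feeds the cost-effectiveness planes and acceptability curves. Adjusting for baseline cost does not remove either error, because both arise after allocation and depend on arm. The sensitivity analyses in section 5.5 address missing data and the choice of RCADS scale, and neither of these points. Without a rule written in advance, overlap would be handled after the data are seen.

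**Working it through.** **1. MOOC hours**

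Inputs from section 4.1.1.1: 3 weeks, 4 hours a week, a 6-hour training day.
- Full completion: 3 x 4 = 12 hours per worker.
- Against the training day: 12 / 6 = 2 times.
- Share of initial learning time: 12 / (12 + 6) = 67%.

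**2. Omitted MOOC cost per ComBAT participant**

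Formula: 12 x hourly cost x workers x uptake / participants in the ComBAT arm. The sample size of 236 at 1:1 (section 3.2) gives 118 per arm. The SAP gives no hourly cost, number of workers or uptake, so these are assumptions:

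| Hourly cost | Workers | Uptake | Cost per ComBAT participant |
|---|---|---|---|
| £25 | 15 | 50% | 12 x 25 x 15 x 0.5 / 118 = £19 |
| £35 | 30 | 50% | 12 x 35 x 30 x 0.5 / 118 = £53 |
| £35 | 30 | 100% | 12 x 35 x 30 x 1 / 118 = £107 |
| £50 | 60 | 100% | 12 x 50 x 60 x 1 / 118 = £305 |

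For scale, full delivery is 8 sessions of 30 to 40 minutes, or 4.0 to 5.3 hours. At £25 to £50 an hour that is about £100 to £267 of contact time per participant.

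**3. Double counting**

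Bias in incremental cost (ComBAT minus usual care) = f_B x n_B x c_B - f_U x n_U x c_U. Here f is the share of sessions reported again in the RUQ-A, n is sessions per participant and c is cost per session. Negative values make ComBAT look cheaper. Eight ComBAT sessions is the SAP's maximum; every other value is assumed, with c_B = £25 and c_U = £60.

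| n_B | f_B | n_U | f_U | Bias |
|---|---|---|---|---|
| 8 | 0 | 6 | 0.8 | 0 - 288 = -£288 |
| 8 | 0.8 | 6 | 0.8 | 160 - 288 = -£128 |
| 8 | 0.5 | 6 | 0.5 | 100 - 180 = -£80 |
| 8 | 0.8 | 2 | 0.8 | 160 - 96 = +£64 |
| 8 | 0.8 | 0 | 0.8 | 160 - 0 = +£160 |

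With equal re-reporting the bias is zero when n_U x 60 = 8 x 25, that is, at 200 / 60 = 3.3 usual-care sessions on average. Above that the error favours ComBAT, and below it the error counts against ComBAT. The SAP does not fix usual-care intensity, so it does not settle the sign.

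**The case against.** **Double counting is possible, not shown.** The RUQ-A wording is not in the SAP and may tell participants to leave out study sessions. Section 5.4 also speaks of treatments and then of other mental health services, so the authors appear to regard the two streams as distinct. This stands as a limit on the finding. It does not close the gap, because section 5.4 gives no means of separating the streams and section 5.3 does not make the distinction at all.

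**The direction is open.** A reader might infer that the double count favours ComBAT, since the named RUQ-A staff look more like usual-care providers than like support workers. The SAP does not support that as a conclusion. ComBAT sessions can be reported through listed or open items, usual care can be nothing at all, and the sign changes within the assumed inputs above.

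**MOOC time is not expressly excluded.** The course is described within the account of training, so the training could be read to include it, and the remarks on charges do not concern staff time. This is a fair alternative reading. The natural one still goes the other way, because the text places the course outside the training and then costs time on the training. The course is also optional, so 12 hours is a ceiling per worker and not an expected value.

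**Netting can remove genuine contacts.** Section 4.1.2 mentions dates only for medications, so RUQ-A contacts cannot be assumed to carry dates. This stands, and it shapes the fix.

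**Conclusion.** The point holds in two parts of different strength.

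- **Overlap.** The total as written can count a treatment contact twice in either arm. Size and direction are unknown: about -£288 to +£160 per participant on assumed session numbers, unit costs and re-reporting rates, and nothing if the RUQ-A already excludes study sessions.
- **MOOC time.** On the natural reading its opportunity cost is omitted. This error has a known direction: it understates ComBAT cost whenever any worker takes the course. The size depends on uptake, hourly cost and participants per worker, none of which the SAP gives. The assumed range is about £19 to £305 per ComBAT participant, which at its upper end matches or exceeds the contact cost of delivery.

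A reader might infer two established errors that both favour ComBAT. Only the second has a direction that the text supports, and even there the omission is a reading of the text and not a stated exclusion. The plan should settle both before analysis.

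**What to change.** 1. In section 5.3, and likewise in section 5.4, state that trial-treatment contacts in both arms are costed once, from treatment records.
2. State whether the RUQ-A instructs participants to exclude study sessions. If it does, one sentence closes this part.
3. If it does not, remove RUQ-A contacts of the same provider type, up to the number of trial sessions recorded for that participant in that follow-up period, before adding RUQ-A costs. Apply the rule alike in both arms. Report results with and without netting, because it may remove some genuine non-trial contacts.
4. In section 4.1.1.1, state that MOOC hours are costed at the worker's hourly rate, using actual completion where recorded. Otherwise show 0, 6 and 12 hours per worker in sensitivity analysis. With £35 an hour and 30 workers, for example, these add £0, £53 and £107 per ComBAT participant.

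The cost is a few sentences of SAP text, one de-duplication step on session records and RUQ-A data already being collected, and a small set of extra runs. No new data collection is required.

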5.4 Secondary analyses

We will undertake incremental cost-effectiveness analyses from mental health service perspective as secondary analyses. The outcome measure of secondary analyses was based on RCADS t-score.

First, we will use the RCADS t-score directly as in the clinical effectiveness analysis. The difference in RCADS t-score at 6 months (primary endpoint) will be estimated following the statistical analysis, using a mixed-effects generalised linear regression model. The model will adjust for RCADS at baseline and include trial group, group-by-time interaction and other baseline covariates as fixed effects, and participants and therapists as random effects to account for repeated measures within participants and possible clustering by therapist.

Secondly, we will calculate the reliable change index (RCI) for RCADS t-score, using standard deviation and Cronbach's α estimated from the pooled sample of both groups at baseline, along with 95% inclusion interval (Equation 1) (14, 15). The change is defined as reliable if the difference in RCADS t-scores between baseline and 6 months is larger than the estimated RCI, otherwise no reliable change. As lower t-scores on RCADS indicate better outcomes, the reliable change is referred to as reliable improvement when the change is deemed reliable and the score at 6 months is lower than at baseline.

Equation 1

$$RCI = SD \times \sqrt{2} \times \sqrt{(1 - \text{Cronbach's } \alpha)} \times 1.96$$

The proportion of participants who make reliable improvement in each group will be calculated. The difference between groups will be calculated by subtracting the proportion in the usual care group from the proportion in the ComBAT group.

The difference in costs of treatments (ComBAT and usual care) and other mental health specific services from baseline to 6 months follow-up will be estimated using generalised linear regression model.

These differences will be used to estimate the incremental costs of ComBAT, comparing with usual care, 1) to reduce one point on RCADS t-score, and 2) to achieve one case of reliable improvement by RCADS t-score.

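### Section 5.3 lets the outcome data choose the covariates, model and random effects of the primary cost, QALY and absent-day analyses, under rules that conflict, and does not say whether the bootstrap respects clustering

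*SAP*

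**What the plan says.** SAP section 5.3 has incremental costs and QALYs "estimated using linear regression, adjusting for costs and utility values at baseline respectively". Beyond those two baseline terms, three steps depend on the outcome data:

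- Covariates: the models also take in "other baseline covariates that show a significant association ($p<0.05$) with dependent variables".
- Model: "The appropriate models will be selected based on AIC and BIC information criteria".
- Random effects: "A Likelihood Ratio test will be used to indicate if random effects should be considered".

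Absent days are to be handled in a similar way. Section 5.3 gives no list of candidate covariates or models, no rule for when AIC and BIC disagree, and no grouping level or significance level for the LR test. Section 5.2 adds that "All analyses will be conducted on the imputed dataset, unless otherwise specified", but does not say how selection is reconciled across imputations.

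Section 5.4 treats clustering differently in one model. Its mixed model for the RCADS t-score has "participants and therapists as random effects to account for repeated measures within participants and possible clustering by therapist", with no preliminary test.

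Confidence intervals, cost-effectiveness planes and acceptability curves come from 5,000 bootstrap resamples of the sample. The unit resampled is not stated.

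**The concern.** The primary incremental cost and QALY feed the acceptability curves and the comparison with the NICE threshold. If covariates, model and error structure are all settled after seeing the outcomes, under rules that can disagree, the SAP does not define one estimate. Two analysts could both follow it and report different ICERs.

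The SAP also accepts in section 5.4 that outcomes may cluster by therapist, yet in section 5.3 any random effect hangs on a test. A non-significant variance test in a trial of this size is weak evidence that clustering is absent. If clustering is real and left out, the intervals are too narrow.

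**Working it through.** **Inputs from the SAP.** "The sample size is set at 236" and "Participants are randomised to either group at 1:1 ratio, using simple randomisation" (section 3.2). The SAP gives no power, SD, dropout, ICC or number of therapists, so 236 cannot be reproduced and everything about clustering below is an assumption shown over a range.

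**1. Do the selection rules agree?** For one added parameter, AIC keeps it if the LR statistic exceeds 2, and P(χ²₁ > 2) = 0.157. BIC keeps it if the statistic exceeds ln(236) = 5.46, and P(χ²₁ > 5.46) = 0.019. The separate screen uses 0.05. A covariate with p between 0.019 and 0.157 is therefore kept by AIC and rejected by BIC.

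**2. How stable is retention?** Take a covariate with true correlation 0.15. By Fisher's z the expected test statistic is atanh(0.15) × √233 = 0.151 × 15.26 = 2.31.

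- AIC, cut √2 = 1.41: Φ(2.31 − 1.41), kept about 81% of the time.
- Screen, cut 1.96: Φ(2.31 − 1.96), kept about 64%.
- BIC, cut √5.46 = 2.34: Φ(2.31 − 2.34), kept about 49%.

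Under the screen, retention is 33% at correlation 0.10 and 87% at 0.20. With 5 to 10 independent null candidates, the chance that at least one enters is 1 − 0.95⁵ = 23% to 1 − 0.95¹⁰ = 40%.

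**3. How far can the estimate move?** In 4,000 simulated trials of 236, a baseline value was always adjusted for and six candidates were screened (assumed coefficients 0.30, 0.20, 0.15, 0.10, 0.10, 0.05).

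- Screening produced 39 different covariate sets; the commonest arose in 21% of trials.
- Across all 2⁶ = 64 possible models (first 300 trials), the gap between the highest and lowest estimate had a median of 0.93 standard errors (5th to 95th percentile 0.50 to 1.59). This is the full span of available answers, not the typical shift that screening causes.
- Type I error was 0.048 with screening and 0.044 with all six fitted.

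**4. What does the LR test do with a real therapist effect?** Assumptions: 236 complete participants, normal outcome, balanced caseloads, therapists nested in arm and clustering in both arms; 200,000 simulations per cell. The test is at 0.05 against the mixture reference (critical value 2.71). At ICC 0.05:

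| Therapists | Per therapist | Design effect | Effect missed | Type I error: test first | Clustering ignored | Always included |
|---|---|---|---|---|---|---|
| 12 | 19.7 | 1.93 | 64% | 0.109 | 0.161 | 0.051 |
| 20 | 11.8 | 1.54 | 68% | 0.084 | 0.114 | 0.050 |
| 40 | 5.9 | 1.25 | 77% | 0.067 | 0.079 | 0.050 |
| 60 | 3.9 | 1.15 | 82% | 0.060 | 0.067 | 0.050 |

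The design effect is 1 + (m − 1) × 0.05, with m = 236 divided by the number of therapists. With the ordinary χ²₁ reference (3.84), 73-89% are missed. At ICC 0.01 about 95% are missed, and at 0.02, 89-93% (mixture reference). At ICC 0.10 the range is 28-53%; with 12 to 20 therapists the effect is kept in 61-72% of trials across both references.

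**5. Would keeping the random effect repair the intervals?** Not if participants are resampled. In 1,000 simulated trials with clustering in the ComBAT arm only, a participant-level percentile bootstrap (400 replicates) gave this coverage without and with the random effect in the estimator:

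- ICC 0.05, 8 per therapist: 0.915 and 0.912.
- ICC 0.10, 8 per therapist: 0.907 and 0.900.
- ICC 0.05, 4 per therapist: 0.939 and 0.929.

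The Monte Carlo standard error is about √(0.91 × 0.09/1,000) = 0.009. In a further simulation with clustering in ComBAT only and 8 per therapist, resampling therapists instead of participants moved coverage from 92% to 93% at ICC 0.05 and from 90% to 94% at ICC 0.10. The first of these differences is too small to lean on.

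**The case against.** The strongest reply is that the selection rules are themselves written down in advance, and that under randomisation covariate selection does not bias the treatment difference. That stands: screening raised neither the type I error nor the standard error in simulation. Adjusting costs and QALYs for different covariates does not bias either difference, and section 5.3 already gives them different baseline terms. The objection does not meet the main point. Rules that disagree, with no list to work from and no order of precedence, do not fix one estimate.

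Several stronger readings are tempting, and the SAP does not support them:

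- *Therapist clustering would usually be dropped from the primary analysis.* Section 5.3 never names therapist as the grouping level, its wording on the LR test is soft, section 5.1 names multilevel software, and no ICC or therapist number is given. At ICC 0.10 with few therapists the test would usually keep the effect.
- *Section 5.4 always includes therapist.* It does so only in the RCADS t-score model. The cost regression in 5.4 states no random effect, and the reliable-improvement comparison is a plain subtraction of proportions.
- *Clustering arises in the ComBAT arm only.* No nesting is specified, and section 4.1.1.2 has professionals in the usual care arm completing session records, so it may arise in both.
- *The choices are made unblinded, and the intervals ignore the selection.* The SAP is silent on analyst blinding and on whether selection is repeated in each bootstrap replicate.

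**Conclusion.** The point holds in two parts.

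First, on the text alone, the primary cost, QALY and absent-day models are built from the outcome data by three steps whose thresholds conflict (0.157, 0.05 and 0.019 for one added parameter at n=236). The consequence is an estimate not fixed in advance, with a median span of about 0.9 standard errors across the models available from six assumed candidates. It is not bias or type I error inflation.

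Second, the SAP recognises possible therapist clustering for RCADS but leaves any random effect in the primary models to a test. If the grouping is therapist and the ICC is up to about 0.05, that test would miss a real effect in most trials (64-82% at 0.05 with 12 to 60 therapists), and type I error at ICC 0.05 would be 0.060 to 0.109. These figures rest on assumed ICCs and caseloads, balanced complete data, and therapists who each work in one arm. Skewed costs, unequal caseloads or one-arm clustering would change them. Because the bootstrap unit is not stated, the intervals and acceptability curves could ignore clustering even where the test keeps it.

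**What to change.** Before data lock, amend section 5.3 as follows.

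1. Name one covariate set for costs, QALYs and absent days: at least baseline cost, baseline utility and the baseline value of the outcome, plus the covariates used in the RCADS model. Write the latter out, since section 5.4 does not list them. Delete the p<0.05 screen and the AIC/BIC choice of covariates.
2. Account for therapist clustering without a preliminary LR test, in each arm where a therapist is recorded. Treat participants who have no therapist as their own cluster.
3. Make the uncertainty match: resample therapists within arm in the bootstrap, or report model-based confidence intervals. Adding the random effect while resampling participants would not do this.

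A fixed list also removes the question of how to reconcile selection across imputed datasets. The change is to SAP wording. Its cost is a few degrees of freedom and slightly wider intervals. In a simulation with eight candidate covariates, a fixed set lost no precision against screening (standard error 0.108 both ways).
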